10.3 Subject Withdrawal and Replacement

Subjects may withdraw from the study at any time and for any reason. If the PI determines that continuing in the study is no longer in the best interest of the subject, then the PI should withdraw the subject from the study. If a subject withdraws from the study, the reason for withdrawal should be documented.

If a subject withdraws from the study before having a biopsy, the subject will be considered a screen failure. If a subject withdraws from the study after having the biopsy, but before injection of NKA, the subject will not be a screen failure, but will not be considered enrolled, and may be replaced. If a subject withdraws from the study after injection but before the end of the follow-up period, the subject cannot be replaced. A maximum of 30 subjects, including subjects previously injected in the two previous Phase 1 trials, will be injected with NKA. Every effort should be made to ensure that patients who have been injected with NKA return for all subsequent follow-up visits and procedures.

11 STUDY VISITS

Subjects will be screened, enrolled, injected and followed according to the Time and Events Schedule and the Time and Events Schedule: Laboratory Assessments.

Before any study specific assessments are performed, the patient must agree to participate in the study by signing the ICF. Informed consent must be obtained following ICH GCP guidelines and 21 CFR Part 50.

11.1 Screening Assessments (Within 45 Days of the Biopsy)

All screening assessments should be scheduled in a timeframe that will allow for scheduling of the biopsy within 45 days of the first screening assessment conducted specifically for this protocol. For example, if a patient signs the consent and then goes to the laboratory for his/her blood draw two days later, then the date of the blood draw would be considered the date of the first screening assessment (not the date the ICF was signed). An MRI study should be conducted as part of the screening assessments. If the patient changes his/her mind after signing the ICF and refuses to have the MRI, then the patient must be discontinued from the study as the MRI will be used to define the dose of NKA.

To qualify for participation in the study, a patient's GFR must be between 20 - 50 mL/min/1.73m² inclusive. To define the GFR for entry criteria, the site should use the eGFR assessed during screening procedures and calculated using sCr and the CKD-EPI equation. If a patient does not meet a specific eligibility criterion, but the Investigator believes that the patient would be an excellent candidate for the trial, then that criterion may be reassessed one time. In general, a patient who does not qualify may be rescreened once as long as the Investigator has sufficient clinical justification for rescreening the patient. If the Investigator has any questions concerning appropriateness of rescreening a patient, then he/she should contact the Medical Monitor.

If, for whatever reason, the biopsy cannot be conducted within 45 days of the screening assessments, then the PI and Medical Monitor should discuss and agree upon the need for repeating screening assessments on a case by case basis. In some cases (e.g., if the biopsy will be a few days out of the protocol specified window), the laboratory assessments performed between 1 and 3 days before the biopsy may be used in place of the screening assessments to satisfy final eligibility criteria. In some cases, it may not be appropriate or necessary to repeat the clinical diagnostic procedures including the ECG or MRI studies.

11.2 Biopsy (4 to 14 Weeks before Injection)

The biopsy should be scheduled within 45 days following the first screening assessment. The biopsy should be scheduled so that the injection procedure can be scheduled at 4 weeks or later. Due to shipping and manufacturing schedules, the preferred days for collecting the biopsy are Wednesday or Thursday. Biopsies should not be collected on a Friday.

Patients should report to the site one to three days before the biopsy for pre-biopsy assessments. As much as possible, pre-biopsy laboratory samples may be collected and assessed to verify patient eligibility prior to biopsy.

Following final review of appropriate eligibility criteria, the biopsy should be performed as described below in Section 12.5.1. The biopsy should be sent to RegenMed (Cayman) Ltd. in the shipping container provided by RegenMed (Cayman) Ltd. according to procedures detailed in the Study Reference Manual. After the biopsy, the patient should remain in the hospital overnight for observation. As long as any biopsy-related AEs have resolved, stabilized, or returned to baseline, the patient may be discharged the same day as biopsy per site standard practice.

Once the biopsy is received at RegenMed (Cayman) Ltd., the biopsy will be assessed and processed according to RegenMed (Cayman) Ltd.'s SOPs for product manufacturing. One to two weeks after receiving the biopsy in North Carolina, RegenMed (Cayman) Ltd. will notify the site concerning the adequacy of the sample for manufacture of NKA. Following the notification to proceed, the site can confirm the injection date. If the biopsy cannot be used for manufacture of NKA, the patient should be discontinued from the study.

11.3 Injection (Study Days -14 to 4)

Due to shipping and manufacturing schedules, NKA injection should be scheduled for Wednesday, Thursday, or Friday. If it is necessary to schedule the injection for Tuesday, the site should contact RegenMed (Cayman) Ltd. before scheduling the injection to make sure Tuesday injection can be accommodated. NKA injection should not be scheduled on a Monday.

Patients should report to the clinic ten to 14 days before the scheduled injection (Day -10 to -14) for pre-injection assessments to verify the continued eligibility of the patient. If the patient is still eligible following review of the results of the assessments, the site will conduct the baseline renal scintigraphy study and contact RegenMed (Cayman) Ltd. indicating that NKA product should be produced. If the patient is not eligible for injection, the site should contact RegenMed (Cayman) Ltd. to alert manufacturing staff not to thaw the patient's frozen renal cells and manufacture NKA. The PI should contact RegenMed (Cayman) Ltd. to discuss the reason(s) the patient did not qualify and determine the best course of action. For example, if the patient was excluded for a temporary condition (e.g., active infection) then it may be possible to manufacture NKA at a later date such that the patient could be injected when he/she became eligible. If the patient's results indicate that it is highly unlikely that the patient would become eligible within an acceptable time frame, then the patient should be discontinued from the study. [Note that in the latter case, the patient can be replaced.] If injection is delayed, the renal scintigraphy study, if conducted, does not need to be repeated prior to injection.

For injection, patients should arrive at the clinic the day of the scheduled injection day (Day 0). The patient should be injected according to procedures discussed below (Section 8.2.2). On Day 1 post-injection, an ultrasound should be performed to verify lack of subclinical adverse effects (e.g., swelling, fluid accumulation). If clinically warranted, an additional ultrasound may be performed prior to discharge to verify lack of subclinical events.

```
Confidential
```

Discharge: After an injection via the percutaneous route, the patient may be discharged the same day if that is the site's usual practice after similar procedures (i.e. percutaneous ablation), after no less than 2 hours of observation and monitoring. If product- or procedure-related AE's occurred following surgery, the patient should not be released from the hospital until the AE's have either resolved, stabilized, or returned to baseline. After a laparoscopic injection, the patient should be observed in hospital for 2 to 4 nights to assess for AEs.

11.4 Follow-up (Days 7, 14, and 28, 2month, 3month, 6month ± 3 days first injection and second injection)

The patient should return to the clinic for follow-up visits one week after injection (Day 7) and on Days 14 and 28. The patient should make every attempt to return for the first follow-up visit on the protocol-specified day (i.e., Day 7) although a 3 day window will be allowed in the case of extenuating circumstances. A 3-day window is allowable for visits on Days 14 and 28, and on Months 2, 3, 6, and 12. At Month 6 visit the same procedures as the pre-injection visit should occur to prepare for the second injection of NKA, if the patient and investigator wish to proceed. The month 6 visit should occur -14 to -10 days before second injection and within 3 days of 6 months post first injection. Patients will return to the clinic Days 7, 14, and 28 after second injection and Months 2, 3, 6, 9, and 12 after second injection.

The monthly visit dates should be calculated using the calendar date of injection. For example, if the patient was injected on April 30^{th} , then the protocol-specified date of the 2 month follow-up visit would be June 30^{th} and the 3 month visit date would be July 30^{th} , etc. The visit window for the long-term monthly follow-up visits is ± 7 days.

End-of-Study Visit (EOS): Patients will complete the EOS Visit as noted below:

- If a patient discontinues the study after having the biopsy but before injection, then he/she should complete all EOS assessments except for the imaging studies; the MRI and/or renal scintigraphy should only be performed if the PI feels one and/or the other would provide critical safety information needed for management of the patient. If the patient has an ongoing study procedure-related SAE, then the patient should not be discontinued until the SAE has resolved, stabilized, or returned to baseline. If the SAE continues for 18 months, then the patient should be discontinued from the study at 18 months and followed as discussed in Section 13.3.3.
- If a patient discontinues from the study after injection but before completing all of the protocol-specified follow-up visits, then he/she should have the EOS Visit at the time of discontinuation. For these patients, the PI will determine whether or not it is clinically prudent to perform one or both of the imaging studies (i.e., MRI and renal scintigraphy). If the patient has a procedure- or product-related SAE(s) that is ongoing, the patient should not be discontinued until the SAE(s) has resolved, stabilized, or returned to baseline. If the SAE(s) is still ongoing at the time of the 18 month visit, the subject should be discontinued from the clinical trial and the SAE followed as discussed in Section 13.3.3.
- Patients who complete all visits including all of the follow-up visits will return at 18 months following second injection for the EOS visit. If the patient has any procedure- or product-related SAE's that are ongoing at the 18 month visit (i.e., not resolved, stabilized

or returned to baseline) the subject should be discontinued from the clinical trial and the SAE followed as discussed in Section 13.3.3.

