- 22. Patients with bleeding disorders that would, in the opinion of the Investigator, interfere with the performance of study procedures; patients taking coumarins (e.g. Warfarin) or other anticoagulants (e.g. enoxaparin or direct thrombin inhibitors).
- 23. Any circumstance in which the investigator deems participation in the study is not in the subject's best interest.
- 24. Use of any investigational product within 3 months of the injection without receiving prior written consent of the Medical Monitor.

Number of Sites: Up to 10 clinical centers will be included in the study.

Study Duration: 18 months NKA injections follow up followed by 24 month long term follow up for a total study duration of 42 months.

Study Enrollment: Up to 30 subjects undergoing NKA injection will be enrolled into the study. Patients who have received a single injection of NKA under previous research protocols may enroll in this clinical trial to receive a single additional injection. Patients who have never received an NKA injection may enroll in this clinical trial for up to a total of two (2) NKA injections, temporally spaced at least 6 months apart. All biopsies are to be taken from a single kidney, and all NKA injections are to be given into the kidney that was biopsied. Patients who complete screening procedures satisfying all I/E criteria will be enrolled into the study immediately prior to the injection. Patients who do not meet all criteria before injection will be considered screen failures. Once a patient has been injected, the patient will have completed treatment and every effort should be made to ensure the patient completes all follow-up visits. Injection dates for the first 3 patients receiving their second NKA injection will be staggered by a minimum of 3 week intervals to allow for assessment of acute adverse events and other safety parameters by the DSMB. Subsequent second injections will continue to be staggered so as to occur no less than 3 weeks apart, but individual DMSB review will not be required. At the completion of the follow-up visits, patients will continue in a long-term follow-up study. Patients will be followed for a total of 36 months following the last NKA injection under this protocol, whether the first or second injection.

Investigational Plan:

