It is anticipated that all patients will be planned to receive 2 injections under this protocol, in order to allow dose-finding and to understand the duration of effect. Under certain circumstances a patient or investigator may decide to postpone or withhold the second dose. In general, if there appears to be any untoward safety risk, in situations including rapid deterioration of renal function, the development of uncontrolled diabetes, or the development of uncontrolled hypertension, or if there is the intercurrent development of a malignancy, the patient should not receive the second dose.

Second injections under this protocol will be staggered so that single injections in different patients occur no less than 3 weeks apart. The DSMB will review the clinical data regarding each of the first 3 second injections under this protocol, and will consult with the Sponsor before the 2nd, 3rd, and 4th second injections are made. Subsequent second injections will continue to be staggered so as to occur no less than 3 weeks apart, but individual DMSB review will not be required.

No staggering will be required for first NKA injections under this protocol.

Post-Injection Follow-up: Subjects will return to the clinic for follow-up safety assessments on Days 7, 14, and 28 post-injection and at 2, 3, and 6 months post-injection. At 6 months post-injection, post-treatment MRI and renal scintigraphy studies will be conducted. After patients complete the 6 month efficacy visit, they will be considered for a second NKA injection. Patients receiving a second dose will follow the same follow up visits that occurred after first injection. Patients 6 month post first injection visit will serve as the patients 14 to 10 day pre- second injection visit. Patients will return for their second injection and at 2, 3, and 6 months post-injection Patients will be followed up to 18 months in the post follow up phase with 6 months after first NKA injection and 12 months after second NKA injection. Refer to the time and events schedule on page 14 for additional post follow up time points.

Long Term Follow-up: Patients will be followed for safety and efficacy for 24 months after the 18 month initial follow up period. Telephone contact will be made 24 and 36 months after the last NKA injection, and visits will be made at 30 and 42 months after the last NKA injection.

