⁶ Conduct End-of-Study (EOS) assessments at the 18 mo visit, or when the subject discontinues from the study (See Section 6.5). Following the EOS visit, the patient should be rolled into the long-term observational follow-up phase.

⁷ The Chemistry panel includes both standard and renal analytes as described in Table 8. Laboratory assessments are described in detail in Section 12.3.

⁸ A urine pregnancy test should be performed using a urine dip-strip; if positive, then a confirmatory test should be performed by the central laboratory.

⁹ Hemoglobin levels must be verified to be > 9 g/dL within 48 hours of each procedure or per site standard practices for verifying Hb levels prior to an injection or surgical procedure.

¹⁰ On procedure days, HCT and Hb should be measured per site standard practice at the site's local lab so the results are immediately available for clinical care. Samples in lab kits for corresponding visit days should be sent to central laboratory for inclusion in database.

¹¹ Prior to injection, test stick should be performed to confirm absence of signs of infection.

¹² β 2-microglobulin should be assessed in both serum and urine samples.

¹³ Research samples (serum/plasma and urine) will be collected, frozen, and stored for assay of renal specific analytes and/or biomarkers at a future date. Results will not be available for reporting in the CSR for this study.

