13.3.2 Recording of Serious Adverse Events

All SAE's should be recorded in the AE CRF from first study procedure through the 6 month follow-up visit. In addition, any SAE's that occur during the long-term observational phase AND are considered related to investigational product, should be recorded in the CRF. All SAE's should be reported according to the procedures discussed below (Section 13.3.4). **13.3.3 Follow-Up of AE's/SAE's**

All AE's that are assessed as related to Investigational Product (i.e., NKA) or study procedures (e.g. biopsy, laparoscopic surgery, or surgical or percutaneous injection) should be followed by the Investigator until the event resolves, stabilizes, or returns to baseline. The investigator should continue to report any significant follow-up information to the Sponsor or Sponsor's designee up to the point the event has been resolved.

SAE's should be followed until the event resolves, stabilizes, or returns to baseline. If the patient insists on discontinuing from the study prior to resolution/stabilization/return to baseline of the SAE, then the patient will continue to be followed as part of the SAE reporting system. That is, the Investigator will continue to follow the patient on a schedule dictated by the clinical situation and submit appropriate follow-up SAE reports as discussed in Section 13.3.4. If the patient refuses to continue to follow-up with the Investigator, then the Investigator may follow the patient through consultation with the patient's primary physician if allowed by the site-approved ICF and applicable regulations.

SAE's that are identified on the last scheduled visit must be recorded in the AE CRF and reported to the Sponsor or Sponsor's designee as outlined in Section 13.3.4. Subjects with unresolved, previously reported serious adverse events, or new serious adverse events identified on the last scheduled visit, should be followed by the investigator until the events are resolved, stabilized, or returned to baseline.

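### Section 11.4 discontinues patients whose related SAE has not settled by Month 18, contradicting the roll-over into long-term follow-up that the plan promises elsewhere without exception

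*Combined protocol and SAP*

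**What the plan says.** Section 11.4, End-of-Study Visit (EOS), third bullet, covers patients who complete every visit. Its trigger is "procedure- or product-related SAE's that are ongoing at the 18 month visit (i.e., not resolved, stabilized", and the sentence continues "or returned to baseline) the subject should be discontinued from the clinical trial", with the SAE then to be followed under Section 13.3.3. The second bullet applies the same rule to patients who stop early after injection and whose related SAE is still open at the 18-month visit.

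Four other places describe what follows Month 18, and none makes an exception for an SAE:

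- Synopsis, Study Duration: "18 months NKA injections follow up followed by 24 month long term follow up for a total study duration of 42 months".
- Synopsis, Study Enrollment: "At the completion of the follow-up visits, patients will continue in a long-term follow-up study". The same paragraph commits to 36 months of follow-up after the last injection.
- Synopsis, Long Term Follow-up: "Patients will be followed for safety and efficacy for 24 months after the 18 month initial follow up period".
- Section 4, laboratory schedule, footnote 6: "Following the EOS visit, the patient should be rolled into the long-term observational follow-up phase".

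On the event itself, Section 13.3.3 says "SAE's should be followed until the event resolves, stabilizes, or returns to baseline".

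**The concern.** Sites hold two instructions for the same patient. If they follow Section 11.4 as written, a harm attributed to the product or procedure decides who leaves scheduled follow-up. That is selection on outcome in a single-arm study of at most 30 patients. Section 14.4.2 rules out imputation, and no sensitivity analysis is planned for patients who leave. Any description of renal function, quality of life or start of renal replacement therapy after Month 18 would then rest on a group from which some of the worst-affected patients had been taken out. Values not collected at the time cannot be recovered later.

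**Working it through.** **1. Is the long-term phase part of the trial?** The Synopsis gives 18 + 24 = 42 months as total study duration, and the figure reproduces. For a new patient with injections 6 months apart, 42 − 6 = 36 months after the last injection, which matches the Study Enrollment commitment. Being discontinued from the trial therefore reaches the long-term phase on a literal reading.

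**2. What would an affected patient lose?**

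| Item | Scheduled follow-up (11.5, schedules) | After discontinuation (13.3.3, 13.3.4) |
|---|---|---|
| The unsettled SAE | Followed | Followed until it settles |
| Later product-related SAEs | Asked about at each contact | Reportable if the investigator learns of them |
| Other AE inquiry | At 24, 30, 36 and 42 months | Not scheduled |
| Renal chemistry, spot urine | At 30 and 42 months | Not specified |
| KDQoL | At 30 and 42 months | Not specified |

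The loss is 4 of 4 scheduled contacts, including both laboratory and KDQoL visits. The timing of the laboratory tests is taken from the Section 4 schedule. Section 11.5 places the specimens at 24 and 36 months, while Section 11.5.2 agrees with the schedule on blood chemistries at 30 and 42; this needs its own correction.

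**3. Which outcomes are exposed?** Windows are from Section 14.3, for a new patient with injections at Months 0 and 6:

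- primary safety: 12 months after the first injection, Month 12;
- primary efficacy: 6 months after the second, 6 + 6 = Month 12;
- secondary laboratory measures: 12 months after the last, 6 + 12 = Month 18.

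All end by Month 18. Treatment-emergent AEs are also summarised only to 18 months (Section 14.7.2). What remains exposed is long-term renal function, KDQoL at 30 and 42 months, and late renal replacement therapy. That last item carries no time limit of its own, although the exploratory objective above it speaks of 12 months.

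**4. How large could the effect be?** The documents give no rate of such SAEs and no difference in decline, so the following is illustration under assumed values.

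Chance of at least one affected patient among 30 is 1 − (1 − p)^30:

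- p = 2%: 45.5%
- p = 5%: 78.5%
- p = 10%: 95.8%

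If k of 30 leave and their eGFR falls faster by d per year, the mean slope of those retained exceeds the mean slope of all 30 by (k/30) × d, in mL/min/1.73m² per year:

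| k | d = 2 | d = 5 | d = 10 |
|---|---|---|---|
| 1 | 0.07 | 0.17 | 0.33 |
| 2 | 0.13 | 0.33 | 0.67 |
| 3 | 0.20 | 0.50 | 1.00 |

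**5. Which Month 18?** The Synopsis builds 18 months as 6 after the first injection plus 12 after the second. Section 11.4 puts EOS at 18 months after the second injection, which is 6 + 18 = 24 months after the first. The rule's own trigger date is therefore unsettled.

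**The case against.** The best reply is that Section 11.4 closes only the 18-month phase. Its first two bullets keep a patient in the study until an SAE settles, with a cap at 18 months, and the third can be read as the same cap. Study Enrollment speaks of a separate long-term follow-up study. Footnote 6 has EOS done at Month 18 or at discontinuation and then rolls the patient over, which on its face includes discontinued patients. This reading is possible, so removal from long-term follow-up is an inference. Against it, every completer finishes the 18-month phase at EOS, so a discontinuation reserved for those with an ongoing SAE does something only if it treats them differently. The Study Duration line also counts the later 24 months in the same study.

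A reader might infer more: that harmed patients disappear from the safety record, or that the sponsor chose to exclude them. The documents do not support either. The sentence itself sends the SAE to Section 13.3.3, and Section 13.3.4 keeps later product-related SAEs reportable at any time, though only if the investigator becomes aware of them. Nor does every unresolved SAE trigger the rule, since one that has stabilised does not. A damaged primary or secondary result cannot be inferred either, as the windows above show.

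**Conclusion.** The point holds as a contradiction between Section 11.4 and the Synopsis and Section 4, footnote 6. On the literal reading, patients with a related SAE that has not settled at Month 18 lose all four scheduled long-term contacts. Long-term renal function, 30- and 42-month KDQoL and late renal replacement therapy could then look better than in all treated patients. The size cannot be derived from the documents; the slope shifts of 0.07 to 1.00 per year rest wholly on assumed numbers of patients and assumed rates of decline, and on all 30 otherwise reaching long-term follow-up. Primary and secondary windows are untouched for a new patient with two injections about 6 months apart. A postponed second injection, with Month 18 counted from the first, would carry the secondary window past that visit.

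**What to change.** Amend the third EOS bullet of Section 11.4, and the matching sentence of the second bullet for patients still attending at Month 18. State that a related SAE ongoing at the 18-month visit does not end scheduled long-term data collection. The patient completes the EOS assessments and enters long-term follow-up under Section 11.5 like other injected patients, and the SAE is followed in parallel under Section 13.3.3. Keep this subject to Section 10.3, so that withdrawal by the patient, or by the investigator in the patient's interest, still applies. In the same amendment, settle whether the 18-month visit is counted from the first injection (Synopsis) or the second (Section 11.4).

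The cost is a few sentences and a few more patients at visits already planned. Long-term results may look slightly less favourable.
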